# **6.7 Reporting of Serious Adverse Events**

All adverse events considered serious, and unexpected shall be reported to

- Emory University IRB within 10 business days if unanticipated and related to Belatacept
- DSMB within 7 days

# 6.8 Data Safety Monitoring Board (DSMB)

A Data Safety Monitoring Board will be established to monitor the safety of the patients during this trial. The initial meeting of the DSMB will occur prior to the start of the study in which study start will be defined as the date on which the first patient enrolled in the study. Subsequent meetings will occur three months from study start and then every six months thereafter. The DSMB will be composed of 3 official members who are members of the Transplant Nephrology, Transplant Surgery, or the Nephrology community. DSMB members must be independent of this study and may not serve as investigators or participate in the care of subjects enrolled in this study. See Appendix 2 for DSMB membership and Appendix 3 for DSMB charter.

DSMB recommendations to modify or prematurely terminate the study shall require a unanimous vote of all voting DSMB members.

To reduce the risk of disclosure of study information to non-DSMB members, board members shall not copy, disseminate, communicate, or allow access to information pertaining to this study. Any copies of materials prepared for distribution to DSMB members will be clearly labeled as confidential. All materials will be identified only with subjects' unique study identification number and personal information that could lead to the identification of the study subject will not be made available to the DSMB membership. All communications and confidential study data will be stored in a secured area by DSMB members.

#### 6.9 DSMB Data Reviews

The initial meeting of the DSMB will commence after the study has been open for 3 months. Subsequent data reviews will occur every 6 months thereafter, until the last study subject has completed study follow-up.

DSMB meetings will be held via teleconference.

Written DSMB reports will be issued following each data review. These reports will be forwarded to the IRB for review with protocol renewals.

# 7. Study design and methods

After randomization into either the q-1M or q-2M dosing groups, belatacept will be administered at a dose of 5 mg/kg, the same dose the patient was taking at the beginning of the study. The visit window for the q1M group will be per standard of care and the visit window for the q2M group will be +/- 5 days. See the attached dosing schedule and budget for the schedule of drug administration and lab tests. Q-2M patients will have lab tests every two weeks starting at week 4 of the study (the first time point when the q-1M patients receive belatacept and theq-2M patients do not). The q-2M group will have labs performed every two weeks from week 4 through week 16. With the exception of every two week labs for the q-2M group from week 4 through week 16 and frequency of belatacept administration, both groups of patients will be treated the same in all ways. Labs will be monthly otherwise. For study purposes, patients will receive a chemistry profile at every lab draw and antibody assessment (PRA/DSA) labs at enrollment, and 6 and 12 months. Otherwise they will be managed per standard of care as clinically indicated. For mechanistic studies, blood and serum will be drawn and stored on select study patients.

# 8. Study Population

The trial population consists of adults ≥18 years of age who are first-time transplant recipients of either living donor or deceased donor renal transplants. Patients of all races and ethnicities will be included.

This is an intention to treat, randomized, controlled trial. There will be a total of 166 subjects, randomized in equal numbers, 83 patients in each arm. We anticipate needing to consent/enroll 200 patients to achieve 166 randomized subjects accounting for an approximate 15% screen failure rate. All patients will be actively followed in the study for 12 months following enrollment. The study is projected to last 2 years.

Before any study procedures are performed, the details of the study will be described to subjects, and they will be given a written informed consent document to read. Patients who consent to participate in the study will sign and date the informed consent document in the presence of study personnel. Only patients who have given informed written consent will be included in this study.

### 8.1 Inclusion criteria

- 1. Adult (age ≥18 years currently),
- 2. first-time renal transplant recipients of either living donor or deceased donor,
  - a. who were initiated on belatacept at the time of transplant and

- b. are at least one year post-transplant and off CNI therapy for at least 6 months.
- 3. patients at low immunologic risk, defined as
  - a. patients with a first transplant who have an antibody screen < 50 against class I and class II antigens,
  - b. no donor specific antibody (DSA),
  - c. who have not had more than one episode of rejection (grade 1A or greater), and
  - d. no episodes of rejection within the last 6 months prior to enrollment, and
  - e. no rejection with a grade of IIB or above.
  - 4. Immunosuppression consisting of belatacept (5mg/kg q 1M), cellcept (at least 1000 mg daily) or equivalent azathioprine dose, and prednisone 5 mg daily.

#### 8.2 Exclusion criteria

- 1. Not first renal transplant, or multi-organ transplant recipient
- 2. History of greater than one episode of biopsy-proven acute rejection (grade 1A or greater), or of rejection of Banff 97 grade IIB or greater, or rejection within the last 6 months.
- Pregnancy (women of childbearing potential must use adequate contraception during study)
- 4. GFR less than 35.
- 5. Serum creatinine at enrollment over 30% higher than 3 months (±4 weeks) prior to randomization
- 6. HbA1C greater than 8 within 3 months of enrollment (diabetic patients only)
- 7. Recent history of significant proteinuria (protein/Cr ratio >1)
- 8. Non-standard belatacept dosing (e.g. dose other than 5 mg belatacept/kg body weight)
- 9. Cellcept dose (or azathioprine equivalent) less than 500 mg po bid.
- 10. Prednisone dose greater than 5 mg po qd within 3 months of enrollment
- 11. Patients not currently taking prednisone
- 12. Active infection, or antibiotic or antiviral drug therapy within 1 month of randomization
- 13. Evidence of CMV viremia or clinical CMV infection within last 3 months.
- 14. BK PCR log greater then 4.3 (copy number greater than 20,0000) within 3 months of randomization
- 15. Known hepatitis B surface antigen-positive or PCR-positive for hepatitis B (testing not required)
- 16. Known HIV (testing not required)
- 17. Presence of donor specific antibody by Luminex single antigen assessment, or antibody screen above 50%.
- 18. History of substance abuse or psychiatric disorder not compatible with study adherence and follow up.

# 9. Study Procedures and Assessments

# See Appendix 3.

# 10. Statistical Analysis

All analyses will be conducted on the intent-to-treat (ITT) population. The distribution of continuous outcome measures will be examined, and non-parametric equivalents of the two-sample t-test will be used to assess the statistical significance of non-normally distributed outcomes.

Statistical significance of the mean difference in eGFR between the q-4 and q-8 treatment groups at 12 months post-randomization will be assessed using the two-sample independent t-test statistic. The incidence of clinically suspected or biopsy-proven acute rejection (and date of acute rejection) will be collected based upon final ETC biopsy-proven acute rejection. We will describe acute rejection rates at 6 and 12 months post-randomization for the overall cohort and for the q-1M and q-2M treatment groups by calculating time to acute rejection. Kaplan-Meier analyses examining time to acute rejection will be used for comparisons by treatment group, with the log-rank test used to assess statistical significance. Potential differences in the severity of acute rejection between the treatment groups will be assessed by comparing the proportions of grade IIA and lower rejections and grade IIB and higher rejections between the treatment groups. Statistical significance of acute rejection severity will be assessed using the two-sample independent t-test statistic.

The incidence of infection in the q-4 and q-8 treatment groups will be collected based on labs performed at regular intervals throughout the study duration. Differences in the incidence of infection by treatment group will be assessed using the two-sample t-test statistic. The incidence of death and graft loss will also be determined, and the death rate and graft loss rates will be calculated at 6 and 12 months post-randomization. Kaplan-Meier analyses examining time to death and time to graft loss will be used for comparisons by treatment group, with the log-rank test used to assess statistical significance.

The incidence of HLA donor specific antibodies (DSA) (e.g. presence or absence of HLA DSA) at 6 and 12 months post-randomization will be compared by treatment group, with statistical significance assessed using the two-sample independent t-test statistic. The frequency of clinic visits, hospitalizations, and transplant biopsies will be calculated for each patient and descriptive statistics (e.g. mean and standard deviation) reported by treatment group. Differences in the frequency of these outcomes at 12 months post-randomization will be compared by treatment groups using the two-sample t-test statistic.

The total cost associated with the q-1M and q-2M dosing intervals will be compared between the two treatment groups by calculating the mean total cost of infusions received by each subject. The time and cost associated with roundtrip travel to the ETC will be estimated using the distance between the residential addresses of subjects and the ETC. Statistically significant differences in the preceding secondary endpoints will be assessed using the two-sample

independent t-test statistic. Potential differences in patient compliance will be assessed using the two-sample independent t-test statistic to compare the proportions of missed infusion appointments between the q-1M and q-2M dosing treatment groups.

Equivalence testing is used to assess whether "practical equivalence" of the outcome of interest has been achieved between two groups. This study will compare the primary outcome of mean eGFR between the standard q-1M control group and the q-2M treatment group, with the hypothesis that mean eGFR will not vary between the groups by more than a pre-specified acceptable difference, or equivalence margin. In the context of equivalence testing, statistical power represents the probability of detecting a difference at least as large as the equivalence margin.

The mean eGFR at one year post-transplant for patients receiving belatacept at the Emory Transplant Center has been found to be 60.2 ml/min/1.73 m² with a standard deviation of 14.5 ml/min/1.73 m². When patients with an eGFR less than or equal to 35 ml/min/1.73 m² are excluded, the mean eGFR at one year post-transplant has been found to be 61.5 ml/min/1.73 m² with a standard deviation of 13.1 ml/min/1.73 m². Based on this inclusion criterion, the table below details several scenarios of potential sample size for different equivalence margins in order to attain 80% power for a significance level (alpha) of 0.05.

Calculated GFR is a continuous variable and will be assessed at monthly intervals (increasing to every two weeks from week 4 to 16 in the q-2M group) throughout the study. The secondary time points of rejection, death, graft lost, and HLA antibody production will be assessed at 6 and 12 months. Total cost, clinic visits, hospitalizations, biopsies and patient satisfaction will be assessed at 12 months.

Assuming a standard deviation of 13.1 ml/min/1.73 m^2:

Equivalence margin	N per group	Sample Size (total
(ml/min/1.73 m  )		N)
5.0	119	238
5.5	98	196
6.0	83	166
6.5	71	122
7.0	61	122

For example, assuming the standard deviation for eGFR at one year post-transplant is 13.1 ml/min/1.73 m^2, 166 patients total (83 per treatment group) are required to be 80% sure that a

two-sided 95% confidence interval will exclude a difference in mean eGFR between the treatment groups of more than 6.0 ml/min/1.73 m^2.

This study also aims to compare the secondary outcome of acute rejection rate between the q-1M and q-2M dosing interval groups. The one-year post-transplant acute rejection rate among patients treated with belatacept is expected to be 1-2%; based on this assumption, the table below details several scenarios of potential sample size for absolute differences in acute rejection rate in order to attain 80% power for a significance level of 0.05.

AR rate for reference group	AR rate for intervention group	Absolute difference	N per group	Sample Size
(q-4)	(q-8)	difference		(total N)
1%	4%	3%	137	274
1%	5%	4%	77	154
1%	6%	5%	49	98
1%	8%	7%	25	50
2%	5%	3%	270	540
2%	7%	5%	97	194
2%	8%	6%	68	136
2%	9%	7%	50	100

Outcome data will be presented to the safety monitoring board for review. The board will consist of a transplant nephrologist, a transplant surgeon and one other medical personnel with sufficient transplant knowledge to monitor the progress of the study; these individuals will not be affiliated with the study. The board will be notified of all serious adverse events, as well as data pertinent to patient recruiting and outcome.

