# 2. Study Objectives

# 2.1 Primary Objective

The primary objective of this non-inferiority trial involving immunologically low-risk patients is to show that the GFR 12 months post-randomization is the same for patients who receive belatacept at q-4 and q-8 dosing intervals.

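### The primary 12-month eGFR test has no rule for patients who die, lose the graft or lack a 12-month value; if q-2M had more losses, non-inferiority would be easier to claim

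*Combined protocol and SAP*

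**What the plan says.** Section 2.1 frames the aim as non-inferiority: "The primary objective of this non-inferiority trial involving immunologically low-risk patients is to show that the GFR 12 months post-randomization is the same" in the two dosing groups. Section 10 states the population, "All analyses will be conducted on the intent-to-treat (ITT) population", and the primary test: "mean difference in eGFR between the q-4 and q-8 treatment groups at 12 months post-randomization will be assessed using the two-sample independent t-test statistic". (Here q-4 and q-8 are labels for the q-1M and q-2M arms.) The only alternative offered is that "non-parametric equivalents of the two-sample t-test will be used to assess the statistical significance of non-normally distributed outcomes", with no rank given for a patient without a value.

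Death and graft loss appear as separate secondary outcomes: "The incidence of death and graft loss will also be determined", and "Kaplan-Meier analyses examining time to death and time to graft loss will be used for comparisons by treatment group", with a log-rank test. Section 10 also has calculated GFR assessed monthly.

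There is no missing-data rule, no imputation, no sensitivity analysis and no allowance for losses after randomisation. The roughly 15% in Section 8 is screen failure before randomisation.

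**The concern.** A t-test needs one number per patient. A patient who has died has no 12-month eGFR. For a patient who has lost the graft, the plan does not say what value, if any, counts. The intent-to-treat sentence says who is to be analysed. It does not say what outcome a patient without one receives, so it does not close the gap. Run as written, the test would use observed values only.

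This matters more here than in a superiority trial. The risk being examined is that a longer dosing interval harms the graft. If it did, and some patients in q-2M lost the graft or died as a result, the non-inferiority test would be made among the patients who did better. Leaving the rule open until the data are in also allows it to be chosen with knowledge of which patients it affects.

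**Working it through.** **Inputs, all from Section 10.** Mean and SD: "the mean eGFR at one year post-transplant has been found to be 61.5 ml/min/1.73 m² with a standard deviation of 13.1 ml/min/1.73 m²". Margin 6.0; 83 per arm; sample size set "in order to attain 80% power for a significance level (alpha) of 0.05". The text around the sample-size table refers to a two-sided 95% confidence interval.

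**Assumptions, not in the documents.** The number of losses (deaths or graft losses) per arm, k, and the eGFR score L given to a loss (0 or 10).

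**The plan's own figure.** Two one-sided t-tests at 0.05 each, true difference 0, SD 13.1 and margin 6.0 give 83 per arm (power 80.4%), so the figure reproduces. That method corresponds to a 90% interval. The checks below use the stated two-sided 95% interval, so non-inferiority is shown when its lower limit is above -6.

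**Check 1: false non-inferiority.** Let q-1M have mean 61.5 and no losses. Let the q-2M mean over all 83 patients, with losses scored L, be 55.5, so that the true difference is exactly -6. With k losses left out:

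- upward shift of the q-2M mean = (55.5 - L) × k / (83 - k)
- SE = 13.1 × √(1/83 + 1/(83 - k))
- false non-inferiority = Φ(-1.96 + shift/SE)

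For k = 2 and L = 0: shift = 111/81 = 1.37; SE = 2.05; Φ(-1.96 + 0.67) = Φ(-1.29) = about 10%.

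| q-2M losses k | SE | Shift, L = 0 | False NI, L = 0 | Shift, L = 10 | False NI, L = 10 |
|---|---|---|---|---|---|
| 0 | 2.03 | 0 | 2.5% | 0 | 2.5% |
| 1 | 2.04 | 0.68 | 5% | 0.55 | 5% |
| 2 | 2.05 | 1.37 | 10% | 1.12 | 8% |
| 3 | 2.05 | 2.08 | 17% | 1.71 | 13% |
| 4 | 2.06 | 2.81 | 28% | 2.30 | 20% |

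**Check 2: direction, and the price of scoring losses.** Now let eGFR among patients without loss be the same in both arms (mean 61.5, SD 13.1). Let k2 and k1 be the losses in q-2M and q-1M.

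- Observed values only: difference 0; SE = 13.1 × √(1/(83 - k2) + 1/(83 - k1)).
- Scored: difference d = -(61.5 - L)(k2 - k1)/83. Each arm's variance, with p = k/83, is (1 - p) × 13.1² + p(1 - p)(61.5 - L)².
- Chance of showing non-inferiority = Φ((6 + d)/SE - 1.96).

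For 2 vs 2 at L = 0: the arm SD rises from 13.1 to 16.0; SE = 16.0 × √(2/83) = 2.49; Φ(6/2.49 - 1.96) = 67.5%.

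| Losses, q-2M vs q-1M | Observed only | Scored 0 | Scored 10 |
|---|---|---|---|
| 0 vs 0 | 83.9% | 83.9% | 83.9% |
| 2 vs 0 | 83.5% | 51.2% | 58.1% |
| 4 vs 1 | 82.8% | 31.0% | 40.1% |
| 2 vs 2 | 83.0% | 67.5% | 72.2% |
| 0 vs 2 | 83.5% | 90.9% | 90.9% |

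The observed-value analysis hardly reacts to losses. Each excess q-2M loss moves the scored difference by 61.5/83 = 0.74 at L = 0, or 51.5/83 = 0.62 at L = 10. About 6/0.74 = 8 excess losses at score 0 would therefore use up the whole margin. In a simulation of that case (6,000 runs), observed values still showed non-inferiority about 82% of the time.

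**The case against.** A reader might infer that the plan excludes patients who die or lose the graft. It does not say so. It is silent, and its intent-to-treat sentence and 12-month follow-up of all patients (Section 8) point the other way. Nor does graft loss necessarily remove a value: the documents do not define it or say that chemistry stops after it. Only death certainly leaves no 12-month measurement. The charge that stands is an unspecified rule, with observed values as the likely default.

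A reader might also infer that the bias must favour non-inferiority. The documents give no loss rates, and the second table shows that direction depends on imbalance. At 0 vs 2 losses the observed-value analysis is the stricter one. Rejection by itself does not take patients out: under Section 6.3, q-2M patients converted after rejection stay in the study.

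Nor do the failures vanish from the trial. Death and graft loss are compared by arm, and rejection counts trigger review by the monitoring board. That stands, but the comparisons are separate secondary log-rank tests for which no sample size is given. A non-significant result on a handful of events would not offset a non-inferiority claim that had lost those patients.

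Losses may well be few. Section 10 expects acute rejection of 1-2%, or 0.8 to 1.7 patients per 83, so three or four excess graft losses would exceed all expected rejections in an arm. The upper rows of the first table are the more plausible ones. The error rates there are also false only relative to a difference that counts losses at the assumed score, which is a choice of estimand.

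**Conclusion.** The concern holds as a gap in specification with a conditional bias. The plan does not say how death, graft loss or a missing 12-month eGFR enters the primary analysis, and the test run as written would not cover the full randomised set. If losses were more frequent in q-2M, non-inferiority would be easier to claim: one or two such losses would take a nominal 2.5% error to about 5% or 8-10%, and four to 20-28%. These figures rest on assumed loss counts, none in q-1M, a true difference of exactly -6 including losses, scores of 0 or 10, and the 95% interval. With balanced losses there is no shift in this model. The point should be settled before analysis; it does not show that the trial's conclusion would be wrong.

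**What to change.** In Section 10:

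- Replace the observed-value t-test with a repeated-measures model on the monthly eGFRs already collected, estimating the 12-month difference for all randomised patients. Use the monthly time points common to both arms, since q-2M has extra draws from week 4 to 16.
- Prespecify an analysis that gives graft loss a low eGFR (0, with 10 as an alternative) or a worst rank. The model alone does not do this: it treats missing values as if the earlier course had continued.
- State how death with a functioning graft is handled.
- Require the non-inferiority conclusion to be reported alongside the scored analysis, with the observed-value t-test as supportive.

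The cost is some text and extra analysis; no new data are needed. The scored analysis has less power. With two losses per arm and no treatment effect, about 83% falls to 68% at score 0 or 72% at score 10. Making it the primary analysis is therefore a trade-off that bears on sample size, and a reason to decide its role in advance.

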# 3. Assessment of Efficacy

### 3.1 Primary Outcome Measure

This study will compare the primary outcome of mean eGFR between the standard q-1M control group and the q-2M treatment group, with the hypothesis that mean eGFR will not vary between the groups by more than a pre-specified acceptable difference, or equivalence margin. Difference in eGFR between the q-1M and q-2M treatment groups will be assessed monthly.

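### The primary eGFR analysis is a t-test not tied to the 6.0 margin or to any confidence interval, so the plan sets no rule for success

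*Combined protocol and SAP*

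**What the plan says.** Four parts of the combined protocol and SAP bear on how the primary outcome is judged.

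- **Section 10, test sentence.** The target is "Statistical significance of the mean difference in eGFR between the q-4 and q-8 treatment groups", which "at 12 months post-randomization will be assessed using the two-sample independent t-test statistic". No margin, interval or non-zero null value is given. An earlier sentence in the same section adds that "non-parametric equivalents of the two-sample t-test will be used to assess the statistical significance of non-normally distributed outcomes".
- **Section 2.1.** "The primary objective of this non-inferiority trial involving immunologically low-risk patients is to show that the GFR 12 months post-randomization is the same" under the two dosing intervals.
- **Section 3.1, repeated in section 10.** The hypothesis is that "mean eGFR will not vary between the groups by more than a pre-specified acceptable difference, or equivalence margin". No value is attached to the margin in either place. Section 10 then says that in equivalence testing "statistical power represents the probability of detecting a difference at least as large as the equivalence margin".
- **Section 10, sample size.** A table lists five candidate margins with their sample sizes. An example below it takes SD 13.1 and 83 per arm and says the trial can be 80% sure that a "two-sided 95% confidence interval will exclude a difference in mean eGFR between the treatment groups of more than 6.0" ml/min/1.73 m². Section 8 fixes the total at 166, which corresponds to the 6.0 row.

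**The concern.** A t-test of a mean difference, with no other null value named, asks whether the difference is zero. Section 10 uses the same formula for infection, donor-specific antibodies and visit counts, where it plainly has that meaning. Failing to reject zero does not show that a loss of 6.0 has been excluded, so the named test cannot support either a non-inferiority or an equivalence conclusion. A switch to a rank test would be further off, because no interval is planned that could be compared with the margin.

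The margin text does not fill the gap, because it does not settle on one rule. It leaves open one-sided non-inferiority or two-sided equivalence, and a 90% or a 95% interval. These have different power at the planned size, and a choice left open could be made after the data are seen. The sentence defining power adds to the confusion: it describes the power of a test for a difference. Equivalence power is the probability of concluding equivalence when the arms are truly alike.

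**Working it through.** **Inputs.** 83 per arm (sections 8 and 10); SD 13.1, margin 6.0, 80% power and alpha 0.05 (section 10). The true difference is taken as 0, which the documents do not state.

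**Reproducing the plan's sample size.** Take equivalence by two one-sided 5% tests, that is, a 90% CI inside ±margin. The normal approximation is

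n = 2 × [SD × (z₀.₉₅ + z₀.₉₀) / margin]² = 2 × [13.1 × (1.645 + 1.282) / 6.0]² ≈ 82,

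and the t distribution gives 83. The same t-based calculation returns every per-group figure in the table, while a 95% CI does not:

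| Margin | Plan, N per group | Equivalence, 90% CI | Equivalence, 95% CI |
|---|---|---|---|
| 5.0 | 119 | 119 | 146 |
| 5.5 | 98 | 98 | 121 |
| 6.0 | 83 | 83 | 102 |
| 6.5 | 71 | 71 | 87 |
| 7.0 | 61 | 61 | 75 |

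Non-inferiority at one-sided 2.5% needs 76 per arm for margin 6.0. The figure of 83 therefore matches neither reading of the 95% CI sentence printed below the table.

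**Precision at 83 per arm.** SE = 13.1 × √(2/83) = 2.034 with 164 degrees of freedom. The 95% half-width is 4.015 and the 90% half-width is 3.364.

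**Power under each rule, true difference 0.** The margin is 6.0 / 2.034 = 2.95 standard errors. The formulas below treat the SD as known; the last two columns integrate over the estimated SD.

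| Rule | Approximation | Power at 83 per arm | N per arm for 80% |
|---|---|---|---|
| Non-inferiority, lower 95% limit above -6.0 | Φ(2.95 - 1.97) | 83.5% | 76 |
| Equivalence, 90% CI within ±6.0 | 2Φ(2.95 - 1.65) - 1 | 80.4% | 83 |
| Equivalence, 95% CI within ±6.0 | 2Φ(2.95 - 1.97) - 1 | 67.0% | 102 |

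**Reading non-significance as success.** The t-test is non-significant whenever the observed difference is within ±4.015. At a true loss of 6.0, the chance of this is about 1 - Φ((6.0 - 4.015)/2.034) = 1 - Φ(0.976), or 16.5% by the noncentral t. The non-inferiority rule passes 2.5% of the time at that point, by construction.

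**Where the two disagree.** Non-inferiority by 95% CI needs an observed loss below 6.0 - 4.015 = 1.985. A loss between 1.985 and 4.015 is non-significant yet leaves a loss of 6.0 possible. With the SD treated as known, the chance of landing there is:

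- true difference 0: Φ(-0.976) - Φ(-1.975) = 14%
- true loss of 3: Φ(0.499) - Φ(-0.499) = 38%

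**The case against.** The strongest reply is that the rule is scattered, not absent. Section 10 itself says equivalence testing will be used for mean eGFR, section 3.1 repeats the hypothesis, the adopted 166 points to the 6.0 row, and the example speaks of an interval excluding a difference beyond 6.0. The t-test sentence names no null value, and two one-sided tests also use a t statistic. Nowhere does the plan say that non-significance will count as success, so the 16.5% describes a rule it never states. The 2.5% comparator is also the strictest available: under the 90% CI rule that reproduces the plan's N, the pass rate at a true loss of 6.0 is 5.0%. Finally, most of the text says equivalence, so a non-inferiority rule is not the only faithful repair.

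Much of this is fair. The intent to use a margin is clear, the zero null is an inference from ordinary usage, and the 16.5% is conditional. The choice of framework belongs to the sponsor. What does not follow is that a rule can be read off the text. At least three fit it, with power from 67.0% to 83.5%, and the stated 95% level does not match the sample size under any of them.

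**Conclusion.** The concern holds. The test named for the primary outcome cannot support the conclusion the trial is designed to reach, and the margin text elsewhere does not fix the framework, the confidence level or the limit to be compared. The sentence claiming 80% assurance with a two-sided 95% CI is wrong if read as equivalence, where the figure is 67.0%.

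The power figures assume SD 13.1, a true difference of zero and a 12-month eGFR for all 83 patients per arm; section 8 allows for screen failures but states no allowance for loss after randomization. Power falls if q-2M is truly somewhat worse: at a true loss of 2, the non-inferiority rule passes about 50% of the time (1 - Φ((2 - 1.985)/2.034) = 49.7%, SD treated as known). Because this governs the trial's single primary conclusion, it must be corrected.

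**What to change.** Replace the primary test sentence in section 10 with wording such as:

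> Estimate the q-2M minus q-1M difference in mean 12-month eGFR with a two-sided 95% CI. Conclude non-inferiority if the lower limit is above -6.0 ml/min/1.73 m².

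This agrees with the non-inferiority label in section 2.1, keeps the 95% interval of the sample-size text and has 83.5% power at the planned size. In addition:

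- State one framework and the 6.0 margin in the same terms in sections 2.1, 3.1 and 10.
- If two-sided equivalence is preferred, state the CI level and its power at 83 per arm (80.4% with 90%, 67.0% with 95%), and correct the 80% assurance sentence to match.
- Define power as the probability of the chosen conclusion when the true difference is zero.
- Exempt this endpoint from the non-parametric switch, or name an interval-based alternative, such as a bootstrap CI, compared with the same margin.

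Non-inferiority with a 95% CI, or equivalence with a 90% CI, costs only protocol and SAP wording. Equivalence with a 95% CI at 80% power needs 2 × 102 = 204 patients, 38 more than the planned 166.
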